## AE Expectedness

AEs can be 'Unexpected' or 'Expected'. Expected AEs include Bleeding development of HIT, pain from subcutaneous administration of the drug, and anemia from blood draws.

Unexpected AEs are those AEs occurring in one or more patients participating in the research protocol, the nature, severity, or frequency of which is not consistent with either:

- The known or foreseeable risk of AEs associated with the procedures involved in the research that are described in (a) the protocol-related document, such as the IRB-approved research protocol, any applicable investigator brochure, and the current IRB-approved informed consent document, and other relevant sources of information, such as product labeling and package inserts; or
- The expected natural progression of any underlying disease, disorder, or condition of the patient(s) experiencing the AE and the patient's predisposing risk factor profile for the AE.

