### **Drug Supply and Dose**

Liraglutide will be supplied in the following package sizes containing disposable, pre-filled, multi-dose pens. Each individual pen delivers doses of 0.6 mg, 1.2 mg, 1.8 mg, 2.4 mg or 3 mg (6 mg/mL, 3 mL). The study drug will be purchased from Novo Nordisk.

3 x Saxenda® pen NDC 0169-2800-13  
5 x Saxenda® pen NDC 0169-2800-15

Each Saxenda® pen is for use by a single patient. A Saxenda® pen should never be shared between patients, even if the needle is changed.

To minimize side effects; liraglutide will be titrated over the first month: starting at a dose of 0.6mg daily for 7 days, increasing to 1.2mg on day 8 for the next 7 days, increasing to 1.8mg on day 15 for the next 7 days, increasing to 2.4mg on day 22 for the next 7 days, and then increasing to 3.0mg on day 39 and continuing this dose for the remainder of the study (12-16 weeks total). If a subject is not able to increase dose to 3.0mg, they will be maintained on the highest dose they are able to tolerate, at a minimum of 1.2mg. If a subject is not able to tolerate the medication at all or at a dose of at least 1.2mg, the medication will be discontinued and the subject will not continue in the study.

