### **Warnings and Precautions**

Warnings and precautions include the following Thyroid C-cell Tumors, Acute Pancreatitis, Acute Gallbladder Disease, Serious Hypoglycemia, Heart Rate Increase, Renal Impairment, Hypersensitivity Reactions, and Suicidal Behavior and Ideation.

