### **Destruction**

The sponsor (or designee) will review with the investigator and relevant site personnel the procedures for documenting receipt of IP, as well as the procedures for counting, reconciling IP, and documenting this process. Used (and/or empty) syringes of enoxaparin will be destroyed locally. Unused syringes will be destroyed locally after sponsor's approval for destruction. Documentation of all used and unused drug disposal must be maintained on site for review during monitoring visits.

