## ASSESSING AND REPORTING ADVERSE EVENTS

### Definition

An adverse event is defined as any untoward medical occurrence in a patient or clinical investigation subject administered a pharmaceutical product and which does not necessarily have to have a causal relationship with this treatment. An adverse event can therefore be any unfavorable and unintended sign (including an abnormal laboratory finding, for example), symptom, or disease temporally associated with the use of a medicinal product or protocol-specified procedure, whether or not considered related to the medicinal product or protocol-specified procedure. Any worsening (*i.e.*, any clinically significant adverse change in frequency and/or intensity) of a preexisting condition that is temporally associated with the use of enoxaparin is also an adverse event.

Adverse events may occur during the course of the use of the IP in clinical trials or within the follow-up period specified by the protocol, or prescribed in clinical practice, from overdose (whether accidental or intentional), from abuse and from withdrawal.

**Serious adverse event.** A serious adverse event is an AE occurring during any study phase (*i.e.*, treatment, follow-up), that fulfills one or more of the following criteria:

1. Results in death
2. Is immediately life-threatening
3. Requires in-patient hospitalization or prolongation of existing hospitalization
4. Results in persistent or significant disability or incapacity
5. Results in a congenital abnormality or birth defect
6. Is an important medical event that may jeopardize the subject or may require medical intervention to prevent one of the outcomes listed above

Each AE will be graded for severity per the NCI CTCAE version 4.0, and these criteria must be used in grading the severity of AEs. The criteria can be found at:  
<http://ctep.cancer.gov/reporting/ctc.html>

For those AEs, which are not listed as part of the NCI CTCAE version 4.0, the same grading system should be used, where:

- **Mild** corresponds to an event not resulting in disability or incapacity and which resolves without intervention

- **Moderate** corresponds to an event not resulting in disability or incapacity but which requires intervention
- **Severe** corresponds to an event resulting in temporary disability or incapacity and which requires intervention
- **Life-threatening** corresponds to an event in which the patient was at risk of death at the time of the event

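### Enoxaparin wording left in a liraglutide-only protocol, with a drug-only attribution scale and a last-dose cutoff, leaves the 5-day SAE notice and the AE window unclear

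*Combined protocol and SAP*

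**What the plan says.** All references are to the combined protocol and SAP.

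- **Drug.** Obese participants take liraglutide, and the Duration of Therapy section says lean controls receive no study drug. Under Drug Supply and Dose it comes in "disposable, pre-filled, multi-dose pens".
- **Enoxaparin text.** The Definition section says that worsening of a preexisting condition "temporally associated with the use of enoxaparin is also an adverse event". The Destruction section says "Used (and/or empty) syringes of enoxaparin will be destroyed locally".
- **Expectedness.** The AE Expectedness section says "Expected AEs include Bleeding development of HIT, pain from subcutaneous administration of the drug, and anemia from blood draws". It then defines an event as unexpected when its kind, severity or frequency does not fit the described risks or the course of an underlying condition. The sources of described risk include the protocol, the consent form and the product labeling.
- **Attribution.** The AE Attribution section asks how far an event is related to the study drug. It also sends every SAE to the project manager within 24 hours.
- **Notice and window.** The Procedure for Reporting Adverse Events section records AEs from the signed permission form to the last liraglutide dose. Over the same period, unexpected SAEs at least possibly related to the research go to the Human Investigation Committee within 5 days.
- **Scope of the definitions.** An AE may be "temporally associated with the use of a medicinal product or protocol-specified procedure" and may occur during use of the product "or within the follow-up period specified by the protocol". For SAEs: "A serious adverse event is an AE occurring during any study phase".

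**The concern.** The safety section should tell staff three things about any event: whether it is expected, whether it is related, and whether it falls inside the reporting period. Here the first answer relies partly on text about another drug. The second is framed around the study drug, although much of the bleeding and bruising risk that the protocol describes comes from catheters and glucose sensors. The third ends at a dose that a third of the participants never take.

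The 5-day committee notice depends on all three answers. Two careful coordinators could classify the same serious procedural event differently and each point to a sentence in the protocol. The study enrolls minors from age 15, so the rule for prompt committee notice should have one reading.

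**Working it through.** No power or sample-size figure is involved. The check sets the sections side by side and traces one test case: a serious bleed caused by an IV catheter or a CGM sensor, before the last dose.

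**1. Basis for the expected items.** The Warnings section begins "Warnings and precautions include the following Thyroid C-cell Tumors, Acute Pancreatitis, Acute Gallbladder Disease, Serious Hypoglycemia" and has 8 entries; the Adverse Reactions section has 12. Bleeding and HIT are in neither. HIT appears nowhere else in the visible text and is not in the abbreviation list. Bleeding has a partial basis under Minimizing Risks: bruising from IV insertion, bruising at the sensor site, and temporary bleeding if a broken sensor piece is removed. All of these are minor.

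**2. Expectedness of the test case.** The words on bleeding and HIT have no punctuation between them, so there are two readings.

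| Reading of the phrase | By the list | By the definition |
|---|---|---|
| Bleeding and HIT are separate items (4 items in all) | Expected: no 5-day notice | Unexpected, as more severe than the described risks: notice due if related |
| One item, bleeding linked to HIT (3 items in all) | Procedural bleeding not listed | Unexpected: notice due if related |

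Only the first reading produces a conflict. In that case the section does not say whether the list or the definition takes precedence. The underlying-condition limb does not readily settle it, because coagulopathy is an exclusion criterion.

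**3. Relatedness of the test case.** Definite, Probable and Possible each require two things: a plausible time sequence from study-drug administration, and a known pattern of response to the study drug.

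- Lean controls, 15 of 45 participants (15/45 = 33%), fail the first requirement because they receive no drug.
- Treated participants fail the second when the event is purely procedural. They also fail the first for baseline procedures done before dosing.

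Read strictly, a purely procedural event cannot reach Possible in any participant. The notice rule, however, asks about relation to the research, and the AE definition expressly includes protocol procedures.

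**4. The window.**

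- *Lean controls:* no dose, so no defined end of recording or notice.
- *Withdrawn participants:* the Restarting the Dose section asks them back for final measurements and blood work. If dosing has already stopped, an abnormal result found then is outside the recording period, although the definition allows an abnormal laboratory finding to be an AE.
- *Completers:* the second food task falls in the last week of treatment, so the gap is small.

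**5. The enoxaparin sentence in the definition.** Read literally, it covers no one in this study. The broader sentence before it, on any medicinal product or procedure, would still capture a worsening on liraglutide. The harm is confusion more than lost events.

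**The case against.** The strongest defense is that these are template remnants that competent staff would read past. Much of that stands. The list introduces examples, and the definition that follows already names severity, so a sensible reader would call a serious bleed unexpected. The notice rule already uses the wider idea of relation to the research. All SAEs go to the project manager within 24 hours, with no expectedness test and no last-dose cutoff. The independent monitor evaluates all AEs and SAEs. A general clause sends AEs to the IRB under applicable rules, though it states no deadline.

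The defense does not show that the text settles the matter. No precedence is stated between list and definition, the attribution categories do not match the notice rule, and the window has no end for one group.

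A reader might infer more than the documents support:

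- *That the Definition section is a second, competing logging rule.* It is not. It says when events may occur, and the reporting section is the only recording instruction. No follow-up period after the last dose is specified for completers. What remains is a mismatch in scope and a coverage gap. Deleting the follow-up wording would remove the mismatch but not the gap.
- *That bleeding is certainly listed without limit.* That depends on the missing punctuation.
- *That bleeding and HIT have no basis in any study document.* The consent pages and the product labeling were not available to check.
- *That a count of procedures, or the lean controls' share of them, measures the problem.* It does not. Procedural events fail the attribution test in treated participants too. The number of blood draws is itself unclear, because the Minimizing Risks section has safety labs at weeks 4 and 8 while the Safety Laboratory section lists only screening and end of study.

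**Conclusion.** The point holds as a wording error in operative safety text and should be fixed. Enoxaparin and HIT do not belong in this protocol on the visible evidence. Attribution that covers only the drug does not fit a notice rule about the research. The last-dose cutoff leaves lean controls without an end point and withdrawn participants' return visit uncovered.

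The size is limited to one deadline, the 5-day notice, and to the AE recording window. A reader might infer that serious events would go unreported. The documents do not support that, given the other reporting routes. They give no rate of serious procedural bleeding or of withdrawal, so no number of affected events is claimed.

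The conclusion rests on three assumptions:

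- Bleeding is a separate list item; this matters only for the expectedness conflict.
- The attribution categories are applied as written.
- Withdrawn participants return after dosing has stopped.

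The HIT and enoxaparin errors need none of these.

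**What to change.** - **Definition:** replace enoxaparin with liraglutide.
- **Destruction:** refer to liraglutide pens, and change the next sentence on unused syringes to match.
- **AE Expectedness:** delete HIT. Limit bleeding to the minor procedure-site bleeding or bruising described under Minimizing Risks. Keep injection pain and blood-draw anemia. State that the test on kind, severity and frequency governs over the list. There is no need to add the liraglutide warnings as flatly expected, because the labeling clause already covers known reactions.
- **AE Attribution:** assess relatedness to study drug or study procedures, with category wording that a procedural event can meet.
- **Procedure for Reporting Adverse Events:** run recording and the notice window through each participant's last study visit, naming lean controls and withdrawn participants.

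The cost is one wording amendment and a few more log entries. Endpoints, sample size and visits do not change.

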## AE Attribution

The participating site investigator must attempt to determine if an AE is in some way related to the use of the study drug and define an attribution category. This relationship should be described as follows:

- Definite – The AE *is clearly related* to the study treatment.

The event follows a reasonable temporal sequence from administration of the study drug, the event follows a known response pattern to the study drug and based on the known pharmacology of the study drug, the event is clearly related to the effect of the study drug. The AE improves upon discontinuation of the study drug and reappears upon repeat exposure.

- Probable – The AE *is likely related* to the study treatment.

The event follows a reasonable temporal sequence from administration of the study drug, the event follows a known response pattern to the study drug AND the event cannot have been reasonably explained by an intercurrent medical condition OR the event cannot be the effect of a concomitant medication.

- Possible – The AE *may be related* to the study treatment.

The event follows a reasonable temporal sequence from administration of the study drug and the event follows a known response pattern to the study drug BUT the event could have been produced by an intercurrent medical condition which, based on the pathophysiology of the condition, and the pharmacology of the study drug, would be unlikely related to the use of the study drug OR the event could be the effect of a concomitant medication.

- Unlikely – The AE *is doubtfully related* to the study treatment.  
AE does not have temporal relationship to intervention, could readily have been produced by the patient's clinical state, could have been due to environmental or other interventions, does not follow known pattern of response to intervention, does not reappear or worsen with reintroduction of intervention
- Unrelated – The AE *is clearly NOT related* to the study treatment.

The event is clearly due to causes distinct from the use of the study drug, such as a documented preexisting condition, the effect of a concomitant medication, or a new condition which, based on the pathophysiology of the condition, and the pharmacology of the study drug, would be unrelated to the use of the study. All SAEs will be reported to the project manager within 24 hours of the site becoming aware of the event.

### **Procedure for Reporting Adverse Events**

All AEs will be recorded from the time the permission form is signed through the last dose of Liraglutide. AEs will be recorded on an Adverse Event log at and entered in OnCore within 72 hours of the PI becoming aware of the event.

All AEs will be reported to regulatory authorities, IRB and investigators in accordance with all local applicable laws and regulations.

All SAEs that are unexpected, which occur any time after the patient has consented up to the last dose of Liraglutide that are possibly, probably, or definitely related to the research notify the Yale Human Investigation Committee (within 5 days).

### **Minimizing Risks**

**Intravenous (IV) catheter insertion and blood drawing:** The risks of bruising, clotting, and infection will be minimized by having venipuncture performed by trained and experienced personnel under sterile conditions. To avoid injury due to fainting, the IV will be inserted when the subjects are recumbent. The blood draws during the OGTT will be obtained from the already inserted catheter to minimize discomfort. Subjects will be asked to not participate in other studies which involve blood draws for 8 weeks after study completion. Additionally, nursing staff have been trained to be conscious of minimizing blood loss by re-infusing saline discards.

**Oral Glucose Tolerance Test (OGTT):** We use the Yale-New Haven Hospital (YNHH) standard of care guideline (blood sampling from a peripheral catheter) to re-infuse the blood saline discards. This method is used to prevent physiological anemia. Any symptoms which may occur during the IV catheter placement or OGTT will be addressed appropriately and if further interventions are indicated the proper physician referrals will be made.

**Continuous Glucose Monitor (CGM):** The CGM poses no major risks to the subjects. Participants may feel a mild discomfort (pin prick sensation) during the sensor insertion. Some individuals may experience black and blueness of the skin at the insertion site of the CGM sensor, which resolves by itself in a few days. Redness and discomfort (inflammation) can occur at the sensor insertion site. Rarely sensors may fracture and a small piece may remain under the skin which will need to be removed by one of the study doctors. This may cause mild discomfort, bruising, or temporary bleeding. The CGM catheter will be placed under sterile

conditions by experienced study doctors or nurse practitioner. In case of signs of inflammation or bruise at the sensor insertion site, the sensor will need to be removed immediately and standard care should be applied. The participants will be given our contact information if they have any questions, concerns or problems.

**Liraglutide (study drug):** Screening labs will be done prior to the start of the study to ensure that participants renal and pancreatic (exocrine) function is within normal limits. Phone calls will be done to ensure study drug is being tolerated by participants (as shown in detail in Appendix 1). Safety labs will be drawn at interval time points (weeks 4, 8 and 12-16) to ensure that renal, pancreatic, liver, and thyroid function remains within normal limits. In addition, a urine pregnancy test will be performed at these time points. The participant will be provided with a wallet card that includes the name of the drug and our contact information in the event that the participant receives outside care or experiences side effects and needs to contact us promptly (Appendix 4).

**Confidentiality:** Study participation is voluntary and subjects are informed that they are free to drop out at any time without penalty. All data will be kept confidential except in cases of imminent danger to the participants. Such limits to confidentiality will be clearly explained to participants verbally and in the written consent forms. Confidentiality in regard to collected materials will be maintained via a numbered reference system maintained by the investigators. Subjects' names will appear only on a consent form and a "key" form kept by the Project Director in locked filing cabinets. Only the PI, mentor, and main investigators will have access to any forms specifying both participant name and subject number. All number coded subjective and biological data will be kept in locked offices with access only to investigators and research staff. Furthermore, good clinical and research practice procedures and HIPAA regulations will be followed. No subjects are identified by name in any of the published literature and only by code in major data storage areas. The ASA24 have been designed to be compliant with HIPAA regulations. Both platforms encrypt data and do not collect any identifying data directly from participants.

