## **Safety Laboratory Procedures and Assessments**

Participants' screening/baseline laboratory assessment will include amylase/lipase, creatinine/GFR, lipid profile, TSH, hemoglobin A1c, AST/ALT, calcitonin and hematocrit. If participants' screening laboratories are not within normal range, (they will be excluded from participation in the study.) they will be assessed by the study investigators and decision about participation in the study will be determined on an individual basis. For example, if the AST/ALT are greater than 3x the upper limit of normal the subject will not be included in the study.

- Participants' screening visit will also include a questionnaire to assess suicidality and depression, using the Patient Health Questionnaire (PHQ-9) (Appendix 2). Because the co-occurrence of depression is higher in individuals with obesity, we anticipate that many of our subjects may have minimal to mild depression. Subjects will be excluded from participation in the study if the result of the screen is greater than or equal to 10 (moderate to severe depression). They will also be referred to a psychologist if they score  $\geq 10$ . Any concern for suicide or self harm will be immediately addressed by implementing emergency petition (EP) procedures and/or calling 911.

Obese participants being treated with Liraglutide will have weekly phone calls with the study physicians or nurse practitioner to monitor for any adverse effects. In addition, during the first week, the study physicians or nurse practitioner will follow-up with the participant with two additional phone calls to answer any questions he/she may have about medication administration as well as to discuss any potential side effects.

Participants will be provided with contact information should they need to contact the study physicians or nurse practitioner at any time throughout the study. The participants will be asked to report any side effects or worsening of depression, suicidal thoughts or behavior, and/or any unusual changes in mood or behavior, to the study physicians or nurse practitioner right away.

Obese participants being treated with Liraglutide will have safety laboratory assessments performed at the following interval time points: week 0 (screening labs as above) and week 12-16 (end of study). These labs will include amylase, lipase, AST,

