ALT, calcitonin and a urine pregnancy test. During phone sessions at weeks 4 and 8 to monitor for any adverse events, study personnel will also administer the PHQ-9 to again assess suicidality and any changes in mood. The PHQ-9 will also be administered at the at the second food snack task (week 12-16, end of study). Since the questionnaire relies on patient self-report, all responses will be verified by the PI and the PI will contact the subject to assess whether they need intervention and determine if they can continue in the study or if the drug should be discontinued. If at any time the subject scores  $\geq 10$  on the PHQ-9, they will be referred to a psychologist, and any concern for suicide or self harm will be immediately addressed by implementing emergency petition (EP) procedures and/or calling 911.

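### Two protocol sections disagree on whether liraglutide-treated participants have safety labs and a urine pregnancy test at weeks 4 and 8

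*Combined protocol and SAP*

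**What the plan says.** Safety Laboratory Procedures and Assessments, in the liraglutide treatment chapter, sets the lab time points for treated participants as "week 0 (screening labs as above) and week 12-16 (end of study"). On content it says "These labs will include amylase, lipase, AST", continuing with "ALT, calcitonin and a urine pregnancy test". The next sentence turns to the intermediate weeks: "During phone sessions at weeks 4 and 8 to monitor for any adverse events", staff also give the PHQ-9. No draw or pregnancy test is attached to those sessions.

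Minimizing Risks, in its paragraph on the study drug, provides for labs before the study starts and then says: "Safety labs will be drawn at interval time points (weeks 4, 8 and 12-16) to ensure that renal, pancreatic, liver, and thyroid function" stay within normal limits. It adds that "a urine pregnancy test will be performed at these time points".

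The screening panel in the treatment chapter is wider than the on-treatment list. It comprises "amylase/lipase, creatinine/GFR, lipid profile, TSH, hemoglobin A1c, AST/ALT, calcitonin and hematocrit".

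**The concern.** Both statements are current protocol text. Neither is conditional and neither refers to the other. A site working from the treatment chapter would do one on-treatment check, while the risk section commits to three.

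The checks bear on named risks. Contraindications lists pregnancy. Warnings and Precautions lists acute pancreatitis and renal impairment. Adverse Reactions lists raised lipase among the commoner reactions. Duration of Therapy stops the drug for pancreatitis, which it describes partly by raised amylase or lipase. Participants are 15 to 39 years old. On the shorter schedule, a pregnancy or a laboratory change without symptoms would first be looked for when treatment ends. If that schedule is the intended one, the risk section promises protection that is not delivered.

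**Working it through.** **Inputs**
- Time points: the two sections quoted above.
- Course length T = 12 to 16 weeks, with 3.0 mg from day 29 (Treatment Regimen with Liraglutide; Table 1).
- Treated participants: 30 obese (Study Population).

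**Step 1: find where the sections differ.**

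| Time point | Safety Laboratory Procedures and Assessments | Minimizing Risks |
|---|---|---|
| Before treatment | labs | labs |
| Week 4 | phone session, PHQ-9 | labs, pregnancy test |
| Week 8 | phone session, PHQ-9 | labs, pregnancy test |
| Week 12-16 | labs, pregnancy test | labs, pregnancy test |

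The pre-treatment and final rows agree. Weeks 4 and 8 do not. Blood cannot be drawn by phone, so the treatment chapter is not simply a shorter account of the same schedule.

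**Step 2: count on-treatment checks.** One (week 12-16) against three (weeks 4, 8 and 12-16).

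**Step 3: longest planned interval without a check**, assuming that the week-0 labs coincide with the first dose. The time points are {0, T} and {0, 4, 8, T}.
- T = 12: 12 weeks against max(4, 4, 4) = 4 weeks.
- T = 16: 16 weeks against max(4, 4, 8) = 8 weeks.

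**Step 4: time at full dose before the first on-treatment check, on the planned titration.**
- Treatment chapter, T = 12: days 29 to 84 = 56 days = 8 weeks.
- Treatment chapter, T = 16: days 29 to 112 = 84 days = 12 weeks.
- Risk section: the first check (week 4) falls at the end of titration. The second (week 8) follows days 29 to 56 = 28 days = 4 weeks at 3.0 mg.

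**Step 5: look for another provision that supplies the missing checks.**
- Treated participants "will have weekly phone calls with the study physicians or nurse practitioner to monitor for any adverse effects". These calls pick up symptoms.
- Contraception or abstinence is an entry condition (Exclusion Criteria), not a test.
- The week-10 OGTT lists glucose, insulin and other metabolic measures, and no amylase, lipase, liver enzyme or creatinine (OGTT and Anthropometric Measures).
- The independent monitor reviews adverse event sheets quarterly (Data safety and monitoring plan).

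None of these schedules a mid-treatment safety lab or pregnancy test.

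**Step 6: compare the panels.** The risk section says that renal and thyroid function are followed. The on-treatment list names no creatinine/GFR or TSH, and calcitonin is its only thyroid-related item. Because that list is introduced as what the labs will include, it need not be complete. This is an ambiguity to close, not a second contradiction.

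**The case against.** The strongest case on the other side is that this is a matter of document alignment. Drawing at every listed time point would break no rule, and no document says that mid-treatment labs are required. Treated participants have weekly clinician calls, with two more in the first week. The dose is held for persistent vomiting, dehydration or abdominal pain, and stopped for pancreatitis. The rationale section says that 3.0 mg is approved for obesity at ages 12 to 17, with a safety profile similar to that in adults. All of this stands and limits the consequence. It does not remove the conflict, because symptom calls do not find a silent laboratory change or an unrecognised pregnancy.

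A reader might infer that the protocol leaves the intended schedule undecided everywhere. That goes too far. The cell marks in the Labs row of Appendix 1 are not visible in the text reviewed. Nor is Appendix 3, which Treatment Regimen with Liraglutide describes as a participant sheet on visits and titration. Either might show the intent. The two narrative sections disagree whatever they show.

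A reader might also infer from Appendix 1 that the two-point schedule is the right one, since none of its numbered visits is headed week 4 or week 8. The chart does not support that. It gives weeks 4 and 8 columns of their own, which fit the PHQ-9 sessions and the disputed labs equally well. Its numbered visits also need not cover every in-person contact: the second CGM sensor is placed at 8 weeks, although no numbered visit carries that heading.

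**Conclusion.** The inconsistency is real and needs correcting. It concerns weeks 4 and 8 only. Its size is two of three stated on-treatment checks per treated participant, with a longest unmonitored interval two to three times as long (16 versus 8 weeks, or 12 versus 4). The intervals rest on week-0 labs falling at the first dose; the count of checks needs no assumption.

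The finding does not show that participants are left without safety oversight, or that any rule is broken by doing all the draws. It touches no estimand, power calculation or analysis. What it shows is that a commitment made as a risk-reduction measure is missing from the section that staff would follow to carry it out.

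**What to change.** Amend Safety Laboratory Procedures and Assessments to match Minimizing Risks. After the week-0 screen, list amylase, lipase, AST, ALT, calcitonin and creatinine/GFR, with a urine pregnancy test in females, at weeks 4, 8 and 12-16. Make the Labs row of Appendix 1, and Appendix 3 if it lists visits, agree. Combine the week-8 draw with the second CGM placement. Naming creatinine/GFR settles the renal ambiguity; the same sentence can say whether calcitonin alone is meant by thyroid function.

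The cost at full retention is up to 2 x 30 = 60 small draws. Added in-person contacts are about 30 (week 4 only) if the week-8 sensor is placed in person. That is likely, because Minimizing Risks has a study doctor or nurse practitioner place it. If it is not placed in person, the figure is up to 2 x 30 = 60.

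Only if the investigator confirms that the week 4 and 8 checks were deliberately dropped should Minimizing Risks be changed instead, to week 0 and week 12-16. It should then also say whether renal function is tested on treatment. That costs only wording but gives up the mid-treatment checks.

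Separately, Drug Supply and Dose starts 3.0 mg on day 39, where Treatment Regimen with Liraglutide and Table 1 say day 29. That is its own correction and adds no weight to this point.
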